9.1 General Approach

Continuous variables will be summarized as means (standard deviations), medians (25th and 75th percentiles), minimum and maximum. Number (percentage) of participants in each category will be presented for categorical variables. Comparisons of categorical variables between the two randomized arms or between pre-specified subgroups will be performed using Pearson's chi-square test or Fisher's exact test depending on expected cell sizes; comparisons of continuous variables will be performed using the Wilcoxon rank-sum test.

Unless otherwise stated, all hypothesis tests will be performed using two-sided tests. No adjustment for multiplicity is planned.

All primary statistical analyses will be conducted using the intention-to-treat principle to define treatment assignment, except as indicated.

In addition to the pre-specified subgroup analyses (see Section 9.4), response magnitude analyses may be considered, in which participants are evaluated based on a binary variable indicating improvement or no improvement with respect to a given assessment.

[figure not shown]
Analyses will be performed using SAS software version 9.4 or higher (SAS Institute, Inc., Cary, NC).

9.2 Primary Efficacy Analysis

The primary endpoint of this study is estimated as time to first occurrence of any of its three following components:

- All-cause death
- Non-fatal MI
- Invasive cardiac catheterization without obstructive CAD

Each death will be adjudicated for cause and date by the CEC. Potential MI cases will be adjudicated for MI yes/no, fatal/non-fatal, MI type, and date of MI by the CEC. Cath without obstructive CAD is the absence of obstructive CAD, defined as diameter stenosis $\geq 50\%$ in a vessel ≥ 2 mm both assessed by QCA (or site read if QCA is not available), $FFR \leq 0.80$, or $iFR \leq 0.89$. The catheterization component of the primary endpoint will be determined according to the algorithm diagrammed below:

To derive the catheterization component of the primary endpoint, site, core lab and DCRI entered clinical data present in the clinical EDC will be extracted and processed through a HeartFlow Cath Algorithm to be classified as Obstructive CAD, No Obstructive CAD, Indeterminate, or Incomplete data. Each ICA classified as either Obstructive CAD, No Obstructive CAD, or Indeterminate will undergo individual Medical Monitor review. For ICAs receiving a final classification as confirmed Obstructive CAD or No Obstructive CAD, the results are considered final. For ICAs confirmed by the Medical Monitor as Indeterminate or ambiguous, CEC adjudication will make the final determination. Incomplete ICAs will be reprocessed through the Cath Algorithm once data are complete and query free.

The time from randomization to the first event among the components of the primary endpoint will be measured (in days) for those who experienced an event and calculated as the date of the first event minus the date of randomization + 1. For participants who do not experience any of the primary component events or who withdraw consent or drop out of the study before experiencing an event, time from randomization to the date of last contact + 1 will be used in the analysis, and those participants will be considered as censored observations in the time-to-event analysis. The 12-month analysis will be censored at 395 days (365 days + 30 day visit window) such that only events on or before this time will be counted in the analysis and event free participants with follow-up greater than 395 will be set to 395.

The primary and major secondary endpoint comparisons between the randomized groups in this study will be performed according to the principle of intention-to-treat; that is, participants will be analyzed according to the treatment (evaluation) arm to which they were randomized, regardless of subsequent crossover or post-randomization strategy.

The log-rank a non-parametric test will be the primary statistical methodology to test for outcome differences between precision care arm and usual care arm with respect to the primary composite endpoint. The Cox proportional hazards model will be used to estimate the average treatment effect size using the hazard ratio (HR) and 95% confidence interval (CI) with treatment assignment as the only covariate in the model. The proportionality assumption (constant hazard over time) in the Cox model will be assessed using the cumulative sums of martingale residuals and the Kolmogorov-type Supremum test. Although log-rank statistic (primary method) is robust under non-proportional hazards it's not optimal due to loss of some statistical power. Thus, if the proportional hazards assumption is violated a two-stage procedure will be implemented (Qiu and Sheng 2008). Due to interim analysis conducted by the DSMB, the final analysis type I error rate (α) will be adjusted as $0.05 - \alpha$ spent at any interim analyses. Cumulative event rates will be calculated according to the method of Kaplan-Meier for each randomized arm as a function of time (in days) from randomization to the time of event or censoring + 1, and the estimated event probabilities will be displayed graphically.

As a supportive analysis, adjusted HRs and 95% CIs will be estimated using the Cox proportional hazards model by including pre-specified baseline risk factors as covariates in the model. These covariates will include: age, sex, CAD equivalent (diabetes, history of peripheral artery disease, or cerebrovascular), and intended first test strata: invasive/non-invasive.

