	
initial diagnostic strategy is not allowed in the usual care arm and is prohibited as a subsequent test for the first 45 days after randomization.
 
Precision evaluation: Participants randomized to a precision strategy will then be assigned to either guideline-recommended care without immediately planned testing (low risk) or cCTA with selective FFR_{CT} (for those with elevated risk or known non-obstructive atherosclerosis) using a risk tool based on pre-test clinical characteristics derived from the PROMISE trial and validated in SCOT-HEART trial. As is recommended for all participants, those assigned to guideline-recommended care without planned testing will be treated with preventive and antianginal medical treatment per guideline recommendations and clinical judgment and followed without testing. Participants and their providers will be provided informational resources explaining the safety and rationale of this strategy based on pre-test probabilities and the PROMISE Minimal Risk Score. Participants with documented intractable symptoms despite maximal medical management may undergo cCTA with selective FFR_{CT} at the participant's or site clinician's discretion.
 
Usual Care: For participants randomized to usual care, the participant's care team will select the specific noninvasive stress test (exercise electrocardiogram, stress nuclear imaging [including PET], stress MR, or stress echocardiogram); OR invasive test: (direct to diagnostic catheterization). The use of cCTA as the initial diagnostic strategy is explicitly excluded in this arm and prohibited as a subsequent test for the first 45 days after randomization.
 
In both arms, the participant's care team will be provided with physician and patient informational resources summarizing current recommendations for test interpretation and preventive care. Optimal medical management will be recommended but not mandated in either arm.

Randomization and Stratification	
Participants will be randomized using a 1:1 randomization scheme via an interactive web or voice-based system (IXRS). Randomization will be stratified by intended first test if randomized to usual care, low vs. elevated pre-test risk, and site.
 
Enrollment in the strata of intended noninvasive test first (vs. intended invasive angiography first) will be capped at 90%.

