The current noninvasive diagnostic testing strategies using functional testing have relatively poor accuracy given the low disease prevalence in this population, leading to high rates of false- positive results¹⁸. Specifically, current diagnostic strategies lead to high rates (~50%) of cardiac catheterization without significant obstructive disease or need for revascularization^{5,7}. As described above, incorporating cCTA into testing strategies can reduce the frequency of cardiac catheterization without obstructive disease but tends to increase rates of invasive angiography^{4, 5}.

Non-invasive computationally-derived FFR_{CT} has been developed using resting coronary CT images without the administration of adenosine or change in underlying cCTA protocols¹⁸⁻²¹. The methodology has been previously described elsewhere.²² In short, FFR_{CT} uses the accurate anatomical model of the coronary arteries and myocardium obtained with conventional cCTA and applies the physical laws that govern flow, microcirculatory resistance, coronary branching, and simulated hyperemia. The Navier-Stokes equations that solve for velocity, resistance and pressure for all Newtonian fluids are applied to provide a 3-dimensional pressure map across the coronary tree. This use of computational fluid dynamics generates FFR values from 0 to 1, with ≤ 0.80 considered hemodynamically significant. The values are congruent with invasive FFR, as shown in several prospective validation studies¹⁸⁻²⁰. Finally, the anatomical modeling has been improved by the use of advanced deep and machine learning techniques applied to the large data sets acquired via central analysis.

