The addition of FFR_{CT} may reduce a potential limitation of a cCTA-first approach, excess invasive angiography, by providing both functional and anatomic data. Specifically, FFR_{CT} markedly reduces the false positive rate of cCTA alone vs. invasive FFR adjudicated ischemia with 68% of false positive CT interpretations in the NXT Trial reclassified as true negative. A retrospective analysis from the PROMISE trial in 181 patients with cCTA, cardiac catheterization and FFR_{CT} revealed that FFR_{CT} was a better predictor of revascularization and events than cCTA alone. Modelling of the incorporation of FFR_{CT} into catheterization decision making suggested a reduction in catheterization rate with cCTA from 12.2% to 7.8% while reducing the rate of catheterization without obstructive CAD from 27% to 15% and increasing the yield of catheterization leading to revascularization from 49% to 61%²³. Given that PCI of lesions with negative FFR is associated with worse outcomes^{24, 25}, while treatment of FFR positive lesions with PCI vs. optimal medical therapy results in improved clinical outcomes, the potential clinical value of adding FFR_{CT} to a cCTA based diagnostic strategy is evident.

The safety and utility of a CT/ FFR_{CT} strategy were further tested in the PLATFORM Study (Prospective Longitudinal Trial of FFR_{CT}: Outcome and Resource Impacts) which evaluated rates of invasive catheterization without obstructive CAD in patients undergoing invasive evaluation. Patients in 2 sequential non-overlapping cohorts of patients referred for ICA were assigned to either undergo ICA or cCTA/ FFR_{CT} with ICA use based on the results of the cCTA and FFR_{CT}. The cCTA/FFR_{CT} strategy resulted in a significant reduction in the rate of cath lab finding of no obstructive disease, from 73 to 12%⁷. Furthermore, ICA was deferred in 61% of cCTA/FFR_{CT} strategy patients. A follow-up at one year demonstrated that cCTA with selective FFR_{CT} strategy yielded similar clinical outcomes and quality of life, at a substantially reduced cost.

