The primary endpoint of this study is based on time-to-first occurrence of any of the components, which is defined as a composite of MACE (all-cause death, non-fatal MI) or invasive cardiac catheterization without obstructive CAD (obstructive CAD defied as diameter stenosis $\geq 50\%$, $FFR \leq 0.80$, or $iFR \leq 0.89$) over 12-month follow-up. The time from randomization to the first event among the components of the primary endpoint will be measured (in days) for those who experienced an event and calculated as the date of the first event minus the date of randomization. For participants who do not experience any of the primary endpoint component events or who withdraw consent or drop out of the study before experiencing an event, time from randomization to the date of last contact will be used in the analysis, and those participants will be considered as censored observations in the time-to-event analysis.

The primary and secondary endpoint comparisons between the randomized groups in this study will be performed according to the principle of "intention-to-treat" (ITT); that is, participants will be analyzed according to the treatment arm to which they were randomized, regardless of subsequent crossover or post-randomization strategy.

The log-rank test⁵³ will be the primary analytic tool for statistically assessing outcome differences between the two randomized treatment strategies with respect to the primary composite endpoint. Cox proportional hazards model⁵⁴ will be used to estimate the hazard ratio (HR) and 95% confidence interval (CI) summarizing the difference in outcome between the two randomized arms, using treatment as the only predictor in the model. Proportionality assumption in the Cox model (i.e., constant hazard over time) will be checked and tested.

Cumulative event rates will be calculated according to the method of Kaplan and Meier⁵⁵ for each randomized arm as a function of time from randomization, and the estimated event probabilities

will be displayed graphically. Adjusted HR and its 95% CI will be estimated using Cox proportional hazards model by including pre-specified baseline risk factors as covariates in the model.

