5.3 Subgroups of Intention-To-Treat and Per-Protocol

Four treatment comparisons will be made.

- Including only Intention-To-Treat participants from the low risk strata
- Including only Intention-To-Treat participants from the elevated risk or known atherosclerosis strata
- Including only Per-Protocol participants from the low risk strata
- Including only Per-Protocol participants from the elevated risk or known atherosclerosis strata

6. Participant Randomization and Enrollment

Once a participant has consented to participate in the trial, participant information will be entered in the database. If a patient is a screen failure, the data that have been collected up until this point for the patient for screening purposes will be entered into the eCRF in the EDC system. No additional information will be collected after this point for such a patient.

Participants who meet all inclusion criteria and none of the exclusion criteria will be randomized in a ratio of 1:1 within a clinical center to either of the following 2 groups using an IXRS.

Precision care - precision care strategy

Usual care- usual care strategy

Randomization will be stratified by intended first test assuming usual care (invasive vs. noninvasive) and by classification as low vs. elevated risk by the PROMISE risk model (see derivation below in Section 6.1). For testing purposes, participants with known non-obstructive coronary atherosclerosis or plaque will be assigned to the elevated risk strata regardless of risk score. The randomization scheme within a clinical center will be carried out by the method of random permuted block design. Participants will be randomized to either the usual care arm or the precision evaluation arm within 14 days of screening. The following tables summarizes the strata:

Summary of Strata

Strata	First Test	Risk
1	Non-Invasive	Low Risk
2	Non-Invasive	Elevated Risk or Known Atherosclerosis
3	Invasive	Low Risk
4	Invasive	Elevated Risk or Known Atherosclerosis

Enrollment in the randomization strata of intended first test being noninvasive (vs. invasive testing or direct to catheterization) will be capped at 90% of the sample size.

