Sample size and power calculations for this study are based on the hypothesis that the precision evaluation arm is superior to the usual care arm on the time-to-first event of the composite 3-component endpoint: all-cause death, non-fatal MI, or invasive cardiac catheterization without obstructive CAD (obstructive CAD defined as diameter stenosis $\geq 50\%$, FFR ≤ 0.80 , or iFR ≤ 0.89) over a 12-month of follow-up. Time to event analysis will use the date of the event, including the date of catheterization at which the absence of obstructive CAD is demonstrated. Assuming 10% of usual care participants will receive angiography as a first test results in an 8% primary endpoint event rate at 1 year in the usual care group and 5% event rate in the precision care group (i.e., 3% absolute [37.5% relative] effect size). Assumptions used in the primary endpoint event rate calculations (i.e., 8% vs. 5%) were: overall 10% will not receive randomized evaluation, and within the precision evaluation arm, approximately 20% will be assigned to guideline-recommended care with symptom management and no planned testing, of whom about 30% will have escalation of care to cCTA with selective FFRCT.

Randomizing 1050 participants per group (2100 total participants) is estimated to provide at least 90% power to detect a relative risk reduction of 37.5% in the precision evaluation arm (see Table 1 below, or refer to the power curves in the protocol). Sample size/power calculations are based on the log-rank test with 12-month accrual period, a minimum 12-month follow-up (i.e. last participant will be followed for at least 12-months), 10% attrition rate (i.e. lost to follow-up, dropouts) and a two-sided type I error rate of 0.05.

The DSMB will review interim analysis data for efficacy as well as possible sample size re-estimation. At any interim analyses, the O'Brien-Fleming boundary generated by Lan-DeMets alpha-spending function will be utilized as a statistical stopping rule (See DSMB charter for more details).

Table 1. The total number of participants needed for 85%, 90%, and 95% power. Although this is not an event-driven study, the table below also provides total number of MACE needed.

1-year event rate in precision evaluation arm	Power	Total number of Primary Events needed	Total number of participants needed
(37.5% ^{2%} effect size)	85%	173	1792
	90%	202	2096
	95%	250	2592

8. Database Sources

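### The primary log-rank test and Cox model ignore the randomisation strata; the test stays valid but gives up power to the extent that intended first test is prognostic

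*SAP*

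**What the plan says.** On allocation, SAP section 6 states: "Randomization will be stratified by intended first test assuming usual care (invasive vs. noninvasive) and by classification as low vs. elevated risk". Its table lists four strata. The final protocol's synopsis adds site: "Randomization will be stratified by intended first test if randomized to usual care, low vs. elevated pre-test risk, and site".

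On analysis, SAP 9.2 makes a log-rank test primary without mentioning strata and reports the "hazard ratio (HR) and 95% confidence interval (CI) with treatment assignment as the only covariate in the model". Protocol VIII.B agrees: "using treatment as the only predictor in the model". The sample size in SAP section 7 also rests on a log-rank test with no strata named, so the documents are consistent with each other. Neither gives a reason for leaving the strata out, and SAP section 11 does not mention the point.

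The factors do appear elsewhere. The supportive Cox model in SAP 9.2 includes intended first test but not risk group. Both are subgroup variables in SAP 4.2.1, and SAP 9.3.4.2 and 9.5 analyse the risk strata separately. None of this alters the primary p-value or hazard ratio.

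**The concern.** Balancing allocation within strata removes between-stratum variation from the treatment comparison. An unstratified log-rank still carries that variation in its variance, so if the strata differ in event rate the test rejects too seldom, under the null and under the alternative.

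Intended first test is likely to be such a factor. In usual care the invasive stratum goes directly to catheterization, and a catheterization without obstructive CAD counts as a primary event. The SAP's own event rate depends on the share: "Assuming 10% of usual care participants will receive angiography as a first test results in an 8% primary endpoint event rate at 1 year". The background in protocol III.A points the same way. It says that "current diagnostic strategies lead to high rates (~50%) of cardiac catheterization without significant obstructive disease or need for revascularization", and in the cited two-cohort study of patients planned for angiography it reports a reduction "in the rate of cath lab finding of no obstructive disease, from 73 to 12" per cent. These are proportions of catheterizations in other populations, not event rates for this trial's strata.

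What is at stake is power, not validity.

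**Working it through.** **Inputs from the documents.** 2100 participants 1:1, one-year rates 8% vs 5%, 10% attrition, two-sided 0.05, 10% invasive-first and about 20% low risk (SAP 7); noninvasive-first enrolment capped at 90% (SAP 6); censoring at 395 days (SAP 9.2).

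**Assumed.** The invasive-stratum rate, constant hazards, 10% loss per year, 100 unequal sites, and permuted blocks of 2 or 4 within site by stratum.

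**1. The plan's own figure.** HR = ln(0.95)/ln(0.92) = 0.6152. Freedman events for 90% power: (1.6152/0.3848)² × (1.960 + 1.282)² = 186 after rounding up. Dividing by the mean event probability over 12 months' uniform accrual plus at least 12 months' follow-up, with 10% yearly loss, gives 2105 participants against the stated 2096. For 85% and 95% power the results are 1800 and 2592 against 1792 and 2592. The stated size is therefore that of an unstratified log-rank. With follow-up cut at 395 days, the same inputs give about 139 events and about 81% power, which is the base for the comparisons below.

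**2. Invasive-stratum rates to consider.** Holding usual care at 8% overall, noninvasive rate = (0.08 − 0.1 × invasive rate)/0.9. One rough anchor comes from protocol III.A. Catheterization without obstructive CAD was 4.3% within 90 days in the functional-testing arm of the cited 10,003-patient trial, and annual event rates are given as about 1-2%. A noninvasive rate of 4.3%, 5.3% or 6.3% implies an invasive rate of (0.08 − 0.9 × 0.043)/0.1 = 41.3%, and likewise 32.3% or 23.3%. A higher one-year catheterization figure would push the invasive rate lower.

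**3. Change in power from stratifying by intended first test** (percentage points; 15,000 replicates per scenario; standard error of the difference 0.04-0.25). Every scenario totals 8% vs 5%.

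| Invasive usual-care rate | Noninvasive usual-care rate | Common HR | Change, common HR | Change, benefit mainly invasive | Change, benefit noninvasive only | Null rejection, unstratified |
|---|---|---|---|---|---|---|
| 8% | 8.0% | 0.615 | 0.0 | not run | −0.1 | 5.1% |
| 18-20% | 6.9-6.7% | 0.613-0.612 | +0.3 | not run | −1.0 | not shown |
| 23.3% | 6.3% | 0.610 | +0.8 | +1.7 | −1.4 | about 4.4% |
| 32.3% | 5.3% | 0.603 | +2.5 | +4.1 | −2.5 | about 4.4% |
| 41.3% | 4.3% | 0.590 | +4.8 | +7.3 | −4.2 | 3.8% |
| 50% | 3.3% | 0.572 | +7.6 | +10.5 | infeasible | 3.0% |

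The common HR is solved so that the precision arm totals 5%. In the mainly-invasive case the invasive rate falls from 23.3% to 8.3%, 32.3% to 12.3%, 41.3% to 16.3% and 50% to 22%. In the noninvasive-only case the invasive rate is equal in both arms; at 50% the precision noninvasive rate would have to be (0.05 − 0.1 × 0.50)/0.9 = 0. The stratified test rejects a true null 4.7-5.1% of the time throughout.

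Power under a common HR, unstratified to stratified: 81.2% to 82.1% at 23%, 80.7% to 83.2% at 32%, 82.0% to 86.7% at 41%, 82.0% to 89.6% at 50%. Changes in the table were taken before rounding.

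**4. Robustness.**
- A second simulation gave 80.5% to 81.8% at 23%, 80.4% to 83.0% at 32% and 82.2% to 86.7% at 41%.
- Placing 80% of the invasive stratum's hazard in the first 45 days left the gains almost unchanged (0.9 points at 23%, 4.6 at 41%).
- Fixing the within-stratum HR at 0.615, so that the precision total drifts up to 5.1-5.3%, gave 77.3% to 81.1% at 35% and 73.5% to 83.5% at 50%.
- Using all four strata instead of intended first test alone changes power by 0.2 points or less if risk group is not prognostic. It adds 0.1-0.4 points if the low-risk hazard is half the elevated-risk hazard.

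**The case against.** The plan's choice is valid, prespecified and the same in both documents, so this is a choice between two legitimate tests. That is correct.

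The large gains need stratum contrasts that the documents do not support well. Adding 1-2% events to the 4.3% figure gives a noninvasive rate of 5.3-6.3%, hence an invasive rate of about 23-32%. In that band the effect is +0.8 to +2.5 points (common HR), +1.7 to +4.1 (mainly invasive) or −1.4 to −2.5 (noninvasive only). The 90% cap also makes 10% the smallest invasive share if it is enforced. At a 20% share and the same noninvasive rates, the invasive rate is only (0.08 − 0.8 × 0.063)/0.2 = 14.8% to (0.08 − 0.8 × 0.053)/0.2 = 18.8%; the common-HR gain is then about 0.4-1.0 points and the noninvasive-only loss 1.4-2.3. This stands: rows above about 32% are the less credible end, and the sign of the effect is not certain. The adverse pattern is the less likely one, since the two-cohort study found its large reduction among patients planned for angiography, but those cohorts were sequential and not randomised.

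A stratified hazard ratio is conditional on stratum, whereas SAP 9.2 describes an average effect. The interim looks and this provision would also need aligning: "if the proportional hazards assumption is violated a two-stage procedure will be implemented". Both points stand as costs. The supportive model and the subgroup plots do not answer the concern, because they leave the primary test as it is.

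**Conclusion.** The concern holds as an improvement that should be made, not as an error. The primary analysis is valid and never anti-conservative in these scenarios, but it discards a probably prognostic factor that is already recorded at randomisation.

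Under a common hazard ratio and 10% invasive-first, the likely gain is about 1 to 2.5 points of power, with about 0.3 if the invasive usual-care rate is 18-20% and nearly 5 if it reaches 41%. It is nil if the strata have similar rates, and negative by about 1 to 4 points (invasive rate 18-41%) if the benefit is confined to the noninvasive stratum. No single value can be claimed, because the documents give no event rates by stratum. The case for acting is stronger because power with 395-day censoring is already about 81% before any interim alpha is deducted; from a higher base the gains would be smaller. Confidence is medium.

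**What to change.** In SAP 9.2, make the primary test a log-rank stratified by intended first test and risk group as recorded in the IXRS, with the hazard ratio from a Cox model stratified the same way.

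- Do not stratify by site: about 100 sites by four strata, with about 140 events, is too sparse.
- If the invasive/low-risk cell (about 2100 × 0.10 × 0.20 = 42 participants) is judged too small, stratify by intended first test alone, which supplies nearly all the gain.
- Use the same statistic at every interim look. If a look has already been taken with the unstratified statistic, settle the boundary with the DSMB before changing.
- State whether the proportional-hazards check and the two-stage procedure are run with or without strata.
- Keep the unstratified log-rank and the treatment-only Cox model as a sensitivity analysis, and say that the primary hazard ratio is conditional on stratum and assumes one ratio across strata.
- Record the change in SAP section 11 before unblinding.

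The cost is a few sentences and no new data. SAP section 3 says the SAP supersedes the protocol for analysis plans, so protocol VIII.B need not block the change.

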The primary objective of the PRECISE trial is to compare the clinical outcomes, downstream decision making regarding noninvasive testing and invasive angiography, and costs of using a precision care with a usual care strategy in participants with stable symptoms suggestive of coronary artery disease. The precision care will start with a pre-test risk assessment. Participants at low risk will be managed initially without cardiac diagnostic testing. Participants not at low risk and those with known atherosclerosis will undergo cCTA with selective FFR_{CT} as the initial evaluation. These results will inform the decision to use invasive coronary angiography. All participants in the trial will also receive guideline-recommended care with symptom and risk factor management.

This SAP contains definitions of analysis populations, derived variables, and details on the statistical methods for the analyses and summaries of study data for the PRECISE trial. This SAP will supersede the protocol in defining the trial endpoints and analysis plans. Mock ups of tables, figures, and data listings are contained in a separate document. A draft list of planned tables and

figures to be created from the final trial data sets can be found in section 10 of this document. Some of these tables and figures will be created as part of the Clinical Study Report and will not be duplicated in the Statistical Report. Details of the economic endpoints analyses are presented in a separate PRECISE Economics and QoL SAP.

4. Analysis Endpoints

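### SAP 9.2 does not say which test decides the primary result if the proportionality check fails, and the final alpha rule does not account for a switch

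*SAP*

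**What the plan says.** SAP 9.2 opens the testing paragraph with "The log-rank a non-parametric test will be the primary statistical methodology to test for outcome differences". Proportionality is to be assessed with cumulative martingale residuals and a supremum test; no significance level or other threshold is given. The next sentence repeats the label but argues against relying on the test: "Although log-rank statistic (primary method) is robust under non-proportional hazards", it is said to be less than optimal because power is lost. The conclusion drawn is that "if the proportional hazards assumption is violated a two-stage procedure will be implemented", with a literature citation.

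The alpha rule follows directly: "Due to interim analysis conducted by the DSMB, the final analysis type I error rate" becomes 0.05 minus whatever was spent at interim looks. SAP section 7 supplies the spending rule: an O'Brien-Fleming "boundary generated by Lan-DeMets alpha-spending function will be utilized as a statistical stopping rule". The amount spent and the timing are left to the DSMB charter.

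Protocol VIII.B says the log-rank "will be the primary analytic tool for statistically assessing outcome differences between the two randomized treatment strategies" and that proportionality will be checked. It attaches no consequence to a failed check and has no two-stage procedure. SAP section 3 says "This SAP will supersede the protocol in defining the trial endpoints and analysis plans". The planned tables in SAP section 10 contain no two-stage output, and section 11 lists only the added day as a change from the protocol.

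**The concern.** Two readings of 9.2 are possible. In one, the log-rank decides and the two-stage result is reported beside it. In the other, the two-stage result takes over when the check fails. The word that links the power argument to the procedure (a 'thus') suggests takeover, because power matters only for the test that decides. The same section explicitly calls its adjusted Cox model supportive and does not say that of the two-stage procedure.

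Under takeover, the choice of test depends on the same outcome data. When the check passes, the log-rank already uses the full available alpha. When it fails, a second stage sensitive to time-varying differences is looking at the very departure that triggered it. A null trial therefore gets an extra chance to reject that the interim deduction does not pay for. Specifying the switch in advance does not remove this.

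A failed check is plausible here, though this is inference from the design and not from data. Initial tests are due before the 45-day visit, about 10% of usual care is assumed to go straight to angiography, and about 20% of the precision arm is assumed to start without testing, of whom about 30% escalate later. Catheterization is itself an endpoint component, so event timing may differ by arm. At stake is which p-value carries the trial's single primary claim.

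**Working it through.** **The plan's own figure.** SAP section 7 gives 2096 participants and 202 events for 90% power at two-sided 0.05, with 8% vs 5% at one year.
- HR = ln(0.95)/ln(0.92) = 0.615.
- Freedman events = (1.960 + 1.282)² × (1.6152/0.3848)² ≈ 10.51 × 17.62 ≈ 185, taken as 186.
- With uniform 12-month accrual, 12-month minimum follow-up and an exponential dropout hazard of 10% a year, 2096 participants yield 185.2 expected events, a mean probability of 0.08836.
- N = 186/0.08836 ≈ 2105, against 2096 stated. Expected events without attrition are 200.4, against 202 stated.

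The plan is thus powered for a log-rank at the full 0.05, with no allowance for a split or a switch.

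**Error of a gated switch.** Let q be the cut-off of the check, and take the check as independent of the log-rank under the null. Then

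overall error = 0.05(1 − q) + q × P(reject | check fails).

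For any second test this lies between 0.05(1 − q) and 0.05(1 − q) + q. At q = 0.05 the limits are 0.0475 and 0.0475 + 0.05 = 0.0975. If rejection after a failed check has probability 0.05, the total is 0.0475 + 0.0025 = 0.05, which is no inflation.

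**Illustration.** The documents give no cut-off and, apart from the citation, neither the form of the second stage nor its alphas. Assumed: a log-rank first stage; a second stage that takes the largest standardised change-point contrast orthogonal to the log-rank; and an equal split, 1 − √0.95 = 0.0253 per stage. The rule is to reject if either stage rejects when the check fails, and otherwise to use the log-rank at 0.05. There is no interim look. The score-process simulation used 200,000 null trials. The participant-level simulation used 1050 per arm, 6.5% events per arm (midway between 8% and 5%), 10% attrition, about 130 events and 200,000 null trials.

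| q | P(reject given failed check) | Formula | Score-process | Participant-level |
|---|---|---|---|---|
| 0.01 | 0.995 | 0.0495 + 0.0100 = 0.0595 | 6.0% | 5.9% |
| 0.05 | 0.398 | 0.0475 + 0.0199 = 0.0674 | 6.8% | 6.7% |
| 0.10 | 0.244 | 0.0450 + 0.0244 = 0.0694 | 6.9% | 6.9% |
| 0.20 | 0.148 | 0.0400 + 0.0295 = 0.0695 | 6.9% | 6.8% |

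The log-rank alone gives 5.0%. The same two-stage test run unconditionally gives 4.9-5.0%, so the excess comes from the gate and not from the two-stage test. Splits of 4%/1% or 1%/4% give 5.6-7.9%. The participant-level runs stop at 365 days, whereas SAP 9.2 censors at 395; this matters little for null error.

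**With one interim look** (timing assumed; equal split of the final level). Spend = 4 × (1 − Φ(2.2414/√t)), and the final level follows the SAP's subtraction.
- t = 0.50: spend 0.0031, final level 0.0469. Overall error: log-rank 4.8%, gated switch 5.7-6.6%.
- t = 0.75: spend 0.0193, final level 0.0307. Overall error: log-rank 3.9%, gated switch 4.6-5.1%.

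**The case against.** The strongest reply is that the log-rank decides. SAP 9.2 labels it primary twice, the second time in the very sentence that raises non-proportionality. Protocol VIII.B agrees, no passage says the two-stage result replaces it, and sections 10 and 11 show neither two-stage output nor a change of primary test. This stands as a lean. It does not settle the matter, because section 3 calls the table list a draft with mock-ups held elsewhere, section 11 does not list the two-stage procedure in any role although the protocol lacks it, and the SAP overrides the protocol on analysis plans.

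Second, the final alpha in 9.2 is not tied to the log-rank by name, so it could be read as capping whichever test is used. That is fair, but a cap on each test does not control the error of choosing between them after looking at the data. The gap is the gate, and nothing wider.

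Third, the sizes rest on assumptions. That also stands.

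A reader might go further and infer three things that the documents do not support:
- That the primary test will run above 5%. This needs both a failed check and the replacement reading.
- That the error approaches 10%. That is the extreme of a bound whose lower end is below 5%, or follows from giving each stage a full 5%, which no passage suggests.
- That the two-stage procedure is undefined. Its form and stage alphas are given by citation and may be fixed in that source, so they are not counted as missing.

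Nor does "No adjustment for multiplicity is planned" in SAP 9.1 help either side: it is a general statement and does not address a gated test.

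**Conclusion.** The point holds as an open decision rule on the primary hypothesis. SAP 9.2 names no threshold for a violation and no deciding p-value after one, and nothing else in the protocol or SAP supplies them. The DSMB charter and table shells were not available.

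The consequence depends on the reading. If the log-rank decides, type I error is at or below 5%, and the missing threshold has no effect on error control. If the two-stage result replaces it after a failed check, the alpha rule does not cover the gate: about 6-7% under the equal-split assumptions without an interim look, less with a late look, and possibly no excess at all, depending on the second test.

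Confidence is high for the open wording and moderate for the impact. The SAP should be corrected on this point, but it is not grounds to doubt the log-rank result itself.

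**What to change.** State in SAP 9.2 that the log-rank, at the alpha left after interim looks, is the sole confirmatory test of the primary endpoint whatever the proportionality check shows. Label the two-stage result supportive, and give the supremum-test threshold that triggers it.

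If the sponsor wants the two-stage test to decide, run it in every case, not gated by the check, with stage alphas that total the available alpha.

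The first option costs only SAP wording and some power against crossing hazards. That loss is not quantified, because the documents give no event-timing data. At the design's 8% vs 5%, the participant-level simulation (40,000 trials) puts the change in power at −1.0 to +2.8 points relative to the conditional switch, over all splits and cut-offs tried. The unconditional option costs more under proportional hazards: 8.5 points with an equal split, 2.7 with 4%/1% and 20.5 with 1%/4%.
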